4.6 Very Low Calorie Ketogenic Diet (VLCKD)

Participants in the experimental arm follow the Very Low-Calorie Ketogenic Diet (VLCKD) for the first 10 weeks of the study. This entails adhering to the VLCKD for 10 weeks while also receiving support from a coach. The coach provides explanations, follow-ups, and moments for progression and reflection throughout this period. The VLCKD begins with a strict phase of 800 kcal/day (consisting of 50g of carbohydrates, >100g of proteins, and low-carb vegetables), followed by a gradual increase in daily calorie intake (1000 kcal, 1200 kcal for women/1400 kcal for men, 1500 kcal for women/1800 kcal for men) based on a Mediterranean diet. For further details on the schedule of contact moments and the content of the VLCKD, please refer to Appendix 2.

4.7 Naltrexone/bupropion

After starting the treatment, the dose should be increased over a 4-week period as follows:

- Week 1: One tablet in the morning
- Week 2: One tablet in the morning and one tablet in the evening
- Week 3: Two tablets in the morning and one tablet in the evening
- Week 4 and onward: Two tablets in the morning and two tablets in the evening

The maximum recommended daily dose of Mysimba is two tablets twice daily with a total dose of 32 mg of naltrexone hydrochloride and 360 mg of bupropion hydrochloride. Patients with too many side effects at high dose may return to the previous dose and continue with it (maximum tolerated dose).

Naltrexone/bupropion need to be taken orally. The tablets should be swallowed whole with some water. The tablets should preferably be taken with some food. The tablets must not be cut, chewed or crushed.

The formulation of naltrexone/bupropion exists of the following:

- Tablet core: cysteine hydrochloride, microcrystalline cellulose, hydroxypropyl cellulose, magnesium stearate, lactose anhydrous, lactose monohydrate, crospovidone type A, indigo carmine aluminium paint (E132), hypromellose, disodium edetate, colloidal silicon dioxide
- Film coating: titanium dioxide (E171), macrogol (3350), talc, indigo carmine aluminium paint (E132)

The package size consists of 112 tablets naltrexone/bupropion.]

4.7.1 Concomitant / Prohibited Medication / Treatment

Permitted:

- Concomitantly used blood glucose-lowering agents. Assess the dose to minimize the risk of hypoglycaemia because treatment with naltrexone/bupropion may result in decreased glucose levels.
- Digoxin. Monitor digoxin levels when used concurrently because bupropion may lower the plasma level of digoxin. Upon discontinuation of naltrexone/bupropion, digoxin levels may increase; monitor patient for possible digoxin toxicity.
- Concomitant administration of a serotonergic agent (SSRI or SNRI). There have been reports of serotonin syndrome, a potentially life-threatening condition. Careful observation is therefore required, especially at initiation and after each dose increase. Watch for changes in mental status,

autonomic instability, neuromuscular dysfunction, and/or gastrointestinal symptoms. If serotonin syndrome is suspected, consider discontinuing treatment.

Not permitted:

- Concomitant treatment with bupropion or naltrexone.
- Concomitant administration of MAO-inhibitors (MAOIs). There should be at least a 14-day period between discontinuation of irreversible MAOIs and initiation of treatment with naltrexone/bupropion. For reversible MAOIs, a 24-hour period is sufficient.
- Opioids such as codeine, loperamide and opioid analgesics, may be less effective. If (temporary) treatment with opioids is necessary, discontinue (or interrupt) treatment with naltrexone/bupropion. Use naltrexone/bupropion cautiously after chronic opioid use has been stopped for 7-10 days, to avoid occurrence of withdrawal symptoms.
- CYP2D6 substrates: Bupropion and hydroxybupropion are CYP2D6 inhibitors. Exposure to drugs metabolized by CYP2D6 may be increased; examples include certain antidepressants (SSRIs and many TCAs, including imipramine, paroxetine, venlafaxine), antipsychotics (haloperidol, risperidone), β -blockers (metoprolol) and class IC antiarrhythmics (flecainide, propafenone). Dose reductions of these agents may be necessary, especially with narrow therapeutic breadth (such as TCAs); consider blood level guided dosing (TDM). Exposure to citalopram increases by about 40%. Tamoxifen may be less effective due to CYP2D6 inhibition.
- Influence on CYP2B6: Bupropion is converted by CYP2B6 to its major active metabolite hydroxybupropion. Use caution with concomitant use of drugs that induce CYP2B6 (e.g., carbamazepine, efavirenz, phenytoin, ritonavir) because the efficacy of bupropion is affected. Use caution with concomitant use of drugs that may inhibit CYP2B6 (e.g., clopidogrel, cyclophosphamide, ifosfamide); the clinical consequences of this interaction are unknown but may decrease the efficacy of bupropion.
- Avoid or minimize the use of alcohol, as neuropsychiatric side effects and decreased alcohol tolerance have rarely been reported with the use of alcohol during bupropion treatment.
- concomitant use of drugs that lower the insult threshold, such as antidepressants, antipsychotics, sedative antihistamines, antimalarial drugs, tramadol, quinolones, theophylline and systemic corticosteroids.
- Concomitant use of levodopa or amantadine, there is evidence of a higher incidence of adverse events (e.g., nausea, vomiting, and neuropsychiatric side effects).

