3.2 Exclusion criteria

Participants eligible for this Trial must **not** meet any of the following criteria:

1. Participant has a history of [type 2 diabetes mellitus (also drugs, HbA1c > 6,5% and FPG >126 mg/dl)]
2. [Female who is pregnant, breast-feeding or intends to become pregnant or is of child-bearing potential and not using an adequate, highly effective contraceptive]
3. Participation in an interventional Trial with an investigational medicinal product (IMP) or device
4. [Not willing to sign informed consent]
5. Younger than 18 years of age at the time of Informed Consent signature
6. Other types of bariatric surgery other than RYGB or SG (including LAGB, BPD)
7. Underwent bariatric surgery (RYGB or SG) with weight regain $< 10\%$ of nadir weight
8. Contraindication for VLCKD, including CKD stage 4-5, liver cirrhosis, type 1 diabetes mellitus, active gout
9. Contraindication for NB including the use of opioids, history of CNS tumor or seizures, severe psychiatric disorder or > 2 psychotropic medications, uncontrolled hypertension
10. Use of other drugs for weight management (e.g. GLP1Ra) in the last 3 months prior to trial intervention
11. Any disorder, which in the Investigator's opinion might jeopardise the participant's safety or compliance with the protocol]

Participants who meet one or more of the above exclusion criteria **must not proceed** to be enrolled/randomized in the Trial and will be identified on the Screening Log as Screen Failure.

4 Study Procedures

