8.4 Protocol / GCP compliance

The Study must be performed in accordance with the protocol, current ICH and ICH-GCP guidelines, and applicable regulatory and country-specific requirements. ICH guidelines are an international ethical and scientific quality standard for designing, conducting, recording, and reporting studies that involve the participation of human participants. Compliance with this standard provides public assurance that the rights, safety, and well-being of Study participants are protected, consistent with the principles that originated in the most recent version of the Declaration of Helsinki, and that the Study data are credible, reliable and reproducible.

The Investigator and Trial team acknowledge and agree that prospective, planned deviations or waivers to the protocol are not permitted under applicable regulations on clinical studies. However, should there be an accidental protocol deviation, such deviation shall be adequately documented in the source documents and on the relevant forms and reported to the CI and Sponsor. Deviations should also be reported to the EC as part of the EC's continued review of the Trial (e.g. through the ASR, APR, etc.). Protocol deviations which are found to frequently recur, will require (immediate) action. The Investigator acknowledges that such recurring protocol deviations could potentially be classified as a serious violation of ICH and/or the protocol.

It is understood that "a serious violation" is likely to affect to a significant degree:

- the safety or physical or mental integrity of the Trial participants; or
- the scientific validity of the Trial

The Investigator is expected to take any immediate action required to protect the safety of any participant included in the Trial, even if this action represents a deviation from the protocol. In such cases, the Sponsor should be notified of this action and the EC at the Trial site should be informed according to local procedures and regulations.

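### Section 4.7.1 permits SSRIs/SNRIs but also bars antidepressants without exception, and nothing says which entry prevails

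*Protocol*

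**What the plan says.** Section 4.7.1 has two lists, headed Permitted and Not permitted.

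- **Permitted.** One entry is "Concomitant administration of a serotonergic agent (SSRI or SNRI"). It warns of serotonin syndrome and adds: "Careful observation is therefore required, especially at initiation and after each dose increase". If the syndrome is suspected, stopping treatment is to be considered.
- **Not permitted, seizure-threshold entry.** This reads "concomitant use of drugs that lower the insult threshold, such as antidepressants, antipsychotics, sedative antihistamines" and goes on to further drug classes. I take *insult threshold* to mean seizure threshold.
- **Not permitted, CYP2D6 entry.** This names SSRIs, many TCAs, paroxetine and venlafaxine as examples of antidepressants whose exposure may rise. It then says how to handle them: "Dose reductions of these agents may be necessary, especially with narrow therapeutic breadth (such as TCAs"), and "Exposure to citalopram increases by about 40" per cent.

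Three other sections bear on the point. Criterion 9 in section 3.2 excludes patients with a "Contraindication for NB including the use of opioids, history of CNS tumor or seizures, severe psychiatric disorder or > 2 psychotropic medications". Section 4.7 sets out the titration, ending in "Week 4 and onward: Two tablets in the morning and two tablets in the evening". Section 8.4 says of an accidental protocol deviation that "such deviation shall be adequately documented in the source documents and on the relevant forms and reported to the CI and Sponsor"; it also requires deviations to be reported to the ethics committee and rules out planned waivers.

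**The concern.** A site following the Permitted entry would start NB in a patient on an SSRI and watch that patient closely. A site following the seizure-threshold entry would withhold NB, or would log the combination as a deviation. Both would be following the protocol's text.

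At stake are the safety instruction for these patients and whether the two sites record the same co-medication in the same way. Section 7.3 dispenses with monitoring by someone independent of the study team, which makes a difference between sites less likely to be noticed.

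**Working it through.** No arithmetic applies. The check is whether the two entries truly collide, and whether anything else in the protocol resolves them.

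1. **Same drugs?** Yes. The CYP2D6 entry itself classes SSRIs as antidepressants and gives paroxetine and venlafaxine (the latter an SNRI) as examples. The word antidepressants in the seizure-threshold entry therefore covers the drugs named in the Permitted entry.

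2. **Same action?** Yes. Both entries concern taking the drug together with NB.

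3. **Same hazard?** No. The permission is tied to serotonin syndrome and the bar to seizure threshold. Criterion 9 makes a history of seizures a contraindication, so the protocol treats seizure risk as important in its own right. A reader cannot assume that a rule for the first hazard disposes of the second.

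4. **Is the bar softened?** Not in its own words. Other entries under the same heading are: CYP2B6 asks for caution, alcohol is to be avoided or kept low, and CYP2D6 gives dose advice. The seizure-threshold entry has no such wording.

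5. **Is there a rule of precedence?** None appears in sections 3.1, 3.2, 4.7, 4.7.1 or 8.4.

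6. **Can such a patient be enrolled?** Yes. Criterion 9 sets its limit at more than two psychotropic medications, so it does not by itself exclude a patient on one SSRI or SNRI.

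7. **When must it be settled?** Before the first tablet. Observation matters most at initiation and after each increase, and the daily dose rises from 1 tablet in week 1 to 1 + 1 = 2 in week 2, 2 + 1 = 3 in week 3 and 2 + 2 = 4 from week 4. In the study flowchart NB starts at the in-clinic randomization visit, and every contact from then until the week 10 clinic visit is remote.

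8. **Does it reach the analysis?** No. Both arms receive NB. Section 6.2 analyses all randomized patients as allocated, whatever their adherence, and defines the per-protocol set by adherence to the allocated treatment without mentioning co-medication. The sample size in section 6.1 uses no co-medication input.

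**The case against.** The strongest reply is that the intended answer can be recovered. The Permitted entry is specific: it names the drug classes, says how to watch the patient and when to consider stopping. The opposing text is one class word in a list of examples, under a heading that does not work as a strict list of bans. A clinician would ordinarily follow the specific entry. This largely stands as evidence of intent. It does not remove the contradiction, because the protocol states no such precedence and the entry in question is worded as a bar.

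It is also fair to say that different logging by the two sites is possible rather than shown, and that section 8.4 is a general rule that does not mention co-medication. Support from criterion 9 is indirect, since it speaks of psychotropic drugs in general and not of antidepressants.

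Three stronger readings are tempting, and the documents do not support them:

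- **That the CYP2D6 entry is a second bar on SSRIs.** It stands under Not permitted, but its dose advice presupposes that the drugs are taken together.
- **That serotonin syndrome is left without a clear rule.** The Permitted entry supplies one.
- **That the per-protocol set or the treatment comparison is compromised.** Neither depends on co-medication, as step 8 shows.

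**Conclusion.** The contradiction is real and visible within one section: the same co-medication is allowed by one entry and prohibited by another. Permitted use is the likely intent, so this is a correction to bring the text into line with that intent, not a challenge to the design. It is still more than a slip of style, because two operative instructions cannot both be followed and the choice falls at the start of treatment.

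The effect is limited to safety conduct and to what counts as a reportable deviation. How many patients it touches cannot be said without a rate of SSRI/SNRI use. The conclusion assumes that *insult threshold* means seizure threshold and that use of a drug listed as not permitted counts as a deviation under section 8.4. The consequence is low, but it is worth correcting because the correction is so small.

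**What to change.** Add to the seizure-threshold entry in section 4.7.1: *except SSRIs/SNRIs, which are permitted with the observation described above*. This agrees with the Permitted entry and with criterion 9, and it changes no eligibility rule, visit, procedure or analysis. The cost is one clause by amendment; under section 8.7 the sponsor judges whether that amendment is substantial.

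No wider regrouping is needed for this. It may look tidy to move the CYP2D6, CYP2B6 and alcohol entries under a heading for drugs allowed with caution, but that alone would create a new conflict. TCAs and antipsychotics appear both in the CYP2D6 entry, with dose-reduction advice, and in the seizure-threshold bar. If the sponsor wants to regroup, it must first decide the status of those two classes, which is a clinical decision and not a matter of wording.

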4.8 Lifestyle

Lifestyle support, excluding the VLCKD, is offered to both the experimental and comparator arms and is regarded as part of the standard care protocol. Consequently, both groups will both have a total of 11 contact sessions, during which 30 minutes will be allocated for individual coaching and routine personal follow-up via telephone. Additionally, there are three modules comprising 12 educational presentations and 12 practical tasks designed for application in everyday life. For a comprehensive schedule outlining specific time points, please refer to Appendix 3.

5 Assessment of Safety

5.1 Adverse Event Reporting

5.1.1 Definitions

5.1.1.1 Adverse Event (AE)

An AE is any untoward medical occurrence in a patient or subject during an experiment, and which does not necessarily have a causal relationship with this treatment.

An AE can therefore be any unfavourable and unintended sign (including an abnormal laboratory finding), symptom or disease temporally associated with the use of a product, whether or not considered related

to the product. Any worsening (i.e., any clinically significant adverse change in the frequency or intensity of a pre-existing condition) should be considered an AE.

5.1.1.2 Adverse Reaction (AR)

An AR is any untoward and unintended responses to an investigational medicinal product or to an experiment and, when an investigational product is concerned, related to any dose administered.

5.1.1.3 Serious Adverse Event (SAE)

An SAE is any untoward medical occurrence that results in any of the following:

- Death
- A life-threatening^a experience
- In-patient hospitalisation or prolongation of existing hospitalisation
- A persistent or significant disability or incapacity
- A congenital anomaly or birth defect
- Important medical events that may be considered an SAE when - based on appropriate medical judgement - they may jeopardise the subject and may require medical or surgical intervention to prevent one of the above outcomes

^a The term "life threatening" in the definition of SAE refers to an event in which the subject was at risk of death at the time of the event. It does not refer to an event which hypothetically might have caused death if it was more severe.

5.1.2 Adverse Events that do not require reporting

In general, the following should not be reported as AEs:

- Pre-existing conditions, including those found as a result of screening (these should be reported as medical history or concomitant illness).
- Pre-planned procedures unless the condition for which the procedure was planned has worsened from the first study-related activity after the subject has signed the informed consent.

The following events are commonly observed and are therefore not considered as adverse events for the purpose of the study:

- Gastrointestinal events (constipation, nausea, vomiting, dry mouth)
- Headache
- Insomnia (especially if naltrexone/bupropion taken at night)

Although these events should not be reported to the Sponsor, these should be recorded in the patient's medical notes according to routine practice.

The following events not to be considered as SAEs are:

- Pre-planned hospitalisations unless the condition for which the hospitalisation was planned has worsened from the first study-related activity after the subject has signed the informed consent.
- Hospitalisation as part of a standard procedure for protocol therapy administration. However, hospitalisation or prolonged hospitalisation for a complication of therapy administration will be reported as an SAE.
- Hospitalisation or prolongation of hospitalisation for technical, practical, or social reasons, in absence of an AE.

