Pharmacotherapy is the last resort for patients before bariatric surgery. The medication used in this trial is naltrexone/bupropion (NB) with extended release. Naltrexone is an opioid antagonist that is currently used in the treatment of dependency, like alcoholism and drug addiction. Bupropion on the other hand is an antidepressant used not only in the treatment of depression but also to reduce cigarette cravings with the ultimate goal of inducing a smoking cessation. A common side effect of bupropion is weight loss. The use of both drugs separately has almost no effect on the patients' weight, but the combination of naltrexone and bupropion has showed a synergistic effect.⁽⁷⁾ NB has promising results in terms of weight loss prior to or post-bariatry with an influence on food intake, cravings and a high sense of satiety.⁽⁸⁾

Conservative therapy may already make a difference, but the majority of patients experience a lack of beneficial effect from this. For these patients, bariatric surgery (BS) may be the solution. Bariatric surgery is considered as the best treatment for morbid obesity (BMI > 40 kg/m² or BMI > 35 kg/m² with one or more weight related comorbidities) in maintaining weight loss.⁽⁹⁾ The biggest weight loss occurs the first year after surgery. Unfortunately, from then on weight stabilization or even weight regain can occur post-bariatry.⁽¹⁰⁾

Despite the fact these patients already tried conservative therapy prior to bariatric surgery, they still benefit to monitor their lifestyle in terms of physical activity, behaviour and dieting. Recent studies show a beneficial role for pharmacotherapy for post-bariatric weight regain.⁽¹¹⁾ Given the mechanism of action of NB, specific benefit can be expected in patients with insufficient reduction or relapse of food cravings and snacking after bariatric surgery. ⁽⁸⁾ Although these possible desirable effects may occur, yet patients may suffer from some side effects of the study drug. The most common adverse events are gastrointestinal disorders (nausea, vomiting, constipation), anxiety, insomnia, agitation and a headache.⁽¹²⁾

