2.3 Secondary Endpoints

- A weight loss percentage at 10 weeks, 16 weeks and at end of trial (= 52 weeks from start)
- A proportion of patients with a weight loss percentage of 5% or more at 10, 16, 26 and 52 weeks
- A proportion of patients with a weight loss percentage of 10% or more at 10, 16, 26 and 52 weeks
- The time to reach a weight loss percentage of 5% and 10%
- The dose of naltrexone/bupropion used at 10, 16, 26 and 52 weeks and at the end of the trial
- The tolerability of VLCKD and NB
- Adherence to VLCKD and NB
- The Patient-Reported Outcome Measures (PROMs) of hunger and cravings at 0, 4, 10, 16, 26 and 52 weeks
- The change in fasting glucose, lipids and blood pressure at 10, 16, 26 and 52 weeks]

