5.1.3 Recording and reporting of Adverse Events

The study-specific visit does not entail any additional risk compared to the routine visit.

Investigators will seek information on AEs during each patient contact. All events, whether reported by the patient or noted by study staff, will be recorded in the patient's medical record and in the (e)CRF within a

reasonable time after becoming aware. If available, the diagnosis should be reported on the AE page, rather than the individual signs or symptoms. If no diagnosis is available, the Investigator should record each sign and symptom as individual AEs.

The following minimum information should be recorded for each AE:

- AE description
- start and stop date of the AE
- severity
- seriousness
- causality assessment to the study interventions
- outcome

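### Section 5.1.2 removes six common complaints from the adverse event record, so a tolerability summary built on AE records would understate side effects

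*Protocol*

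**What the plan says.** Section 5.1.2 names four gastrointestinal complaints (constipation, nausea, vomiting, dry mouth), headache and insomnia, and states: "The following events are commonly observed and are therefore not considered as adverse events for the purpose of the study". It continues: "Although these events should not be reported to the Sponsor", they are to be kept in the medical notes as routine practice dictates.

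Section 5.1.3 sets the recording rule: "All events, whether reported by the patient or noted by study staff, will be recorded in" the patient's "medical record and in the (e)CRF". It adds: "If no diagnosis is available, the Investigator should record each sign and symptom as individual AEs". It then lists six data items under the words "The following minimum information should be recorded for each AE": description, start and stop dates, severity, seriousness, causality and outcome. The diary in section 5.1.3.2, kept for the first 12 weeks, is for AEs and SAEs.

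The background says of the study drug: "The most common adverse events are gastrointestinal disorders (nausea, vomiting, constipation), anxiety, insomnia, agitation and a headache". Section 2.3 lists "The tolerability of VLCKD and NB" as a secondary endpoint, and section 6.2 plans a descriptive analysis of it.

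On SAEs, a bullet in section 5.1.3.2 restricts reporting after week 12 to those causally related to a study-specific intervention. The paragraph that follows requires every SAE, as the protocol defines it, to reach the Sponsor within 24 hours.

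**The concern.** Not reporting expected, non-serious complaints to the Sponsor is a reasonable economy. Section 5.1.2 goes further: it takes away their status as adverse events. The structured data requirements of the protocol (six items per AE, the AE page, the diary) all hang on that status.

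The complaints removed are largely those by which the tolerability of NB would be judged. If tolerability is summarised from AE records, the table would show anxiety and agitation but not nausea, vomiting, constipation, headache or insomnia. The arms could not be compared on these complaints either. An analysis plan written later cannot restore dates and severities that nobody was asked to write down.

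**Working it through.** No sample size or power figure is involved. The check sets the sections side by side and counts.

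1. **Overlap of the two lists.**

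| Complaint | Exempted in 5.1.2 | Common NB event in the background |
|---|---|---|
| Nausea | yes | yes |
| Vomiting | yes | yes |
| Constipation | yes | yes |
| Headache | yes | yes |
| Insomnia | yes | yes |
| Dry mouth | yes | no |
| Anxiety | no | yes |
| Agitation | no | yes |

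Exempted: 6. Named as most common: 7. In both: 5. From the background list, 7 − 5 = 2 remain recordable. This counts terms, not events.

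2. **Effect of the exemption.** The general definition in section 5.1.1.1 covers any unfavourable, unintended symptom associated in time with use of a product, so the six complaints would qualify. Section 5.1.2 takes them out. Section 5.1.3 then asks for 6 data items for each AE, and hence for 0 items for each exempted complaint. The diary does not ask for them either.

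3. **What remains.** A participant who has nausea in the first 10 weeks, keeps the same NB dose and continues would leave no required structured trace. NB dose is collected at 10, 16, 26 and 52 weeks, and the flowchart collects reason for discontinuation. Neither captures a complaint that changed nothing, and the flowchart lists no reason for a dose reduction. The notes are a stated data source (sections 2.4 and 7.1.1.2), but 5.1.2 does not require dates or severity in them.

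4. **Where the data could be collected.** The flowchart schedules an (S)AE assessment at V2 (baseline), W10, W16, W26 and W52: five occasions. With 62 participants, 62 × 5 = 310 checklists at most. If the planned 20% drop-out all fell between V2 and W10, the number would be 62 + 0.8 × 62 × 4 = 260.4, about 260.

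5. **SAEs after week 12.** Take an unrelated, non-fatal hospitalisation after week 12. The bullet in 5.1.3.2 says it is not reported. The next paragraph covers all SAEs as defined, and the definition in 5.1.1.3 carries no causality condition, so read alone it says report within 24 hours. The SAE row of section 5.1.4.2 allows exceptions defined in the protocol but does not identify them. Deaths are reportable in any case under 5.1.3.5.

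**The case against.** The strongest reply is that the protocol nowhere says tolerability will be tabulated from AE records. Its operational definition may properly sit in the analysis plan, and treatment-based measures exist: dose used, return to a previous dose because of side effects, and reason for discontinuation. Section 2.4 also refers to Appendix 4 for the parameters collected, and that appendix is not in the text at hand. This stands as a limit on the claim: understatement follows if AE records are the source, and other sources soften it. It does not remove the point, because the exemption is a data-capture rule fixed in the protocol itself.

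A reader might infer a flat contradiction between 5.1.2, which keeps these complaints in the notes, and 5.1.3, which sends all events to the (e)CRF. The text does not bear that out. Section 5.1.3 concerns adverse events by its heading, the sentence before speaks of seeking AEs, and the sentence after refers to the AE page. All events there most naturally means all AEs, and the specific exemption precedes the general rule. The difficulty is the exemption itself.

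A reader might also infer that the two sites will record differently. Routine notes need not match, but the funding section makes one PhD student accountable at both sites for data collection and adverse event reporting, although with only pseudonymised data from the second. A difference is possible but not shown.

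On SAEs, the week-12 bullet can be read as the exception that 5.1.4.2 allows, with the bullet setting scope and the paragraph setting the deadline. That reading is fair, but the paragraph does not state it. The AE row of 5.1.4.2 is only an overview of deadlines, so its silence about week 12 is no conflict. The length of follow-up after week 12 says nothing about how many events are concerned.

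**Conclusion.** The point holds in a limited form. As written, section 5.1.2 leaves six complaints, covering five of the seven most common NB adverse events in the protocol's own list, without any required date, severity or (e)CRF entry, while tolerability is a secondary endpoint. A summary based on AE records would understate side effects. The amount is unknown, since no event rates are given. This rests on two assumptions: that all events in 5.1.3 means all AEs, and that AE records are the main source for the endpoint.

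It would go too far to conclude that the tolerability endpoint is lost or that safety reporting fails. Dose, discontinuation and notes give partial cover. Serious cases keep an SAE route because the SAE definition rests on any untoward medical occurrence, and deaths are always reported. The exemption is the same in both arms, and the primary endpoint is untouched.

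The SAE wording in 5.1.3.2 is a secondary matter of loose drafting. It can be read as conflicting only for unrelated, non-fatal SAEs after week 12.

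**What to change.** - In 5.1.2, keep the waiver of reporting the listed non-serious events to the Sponsor, and delete the statement that they are not adverse events for the study. Say that the waiver takes precedence over the AE deadline in 5.1.4.2.
- Record the six complaints in the eCRF, identically in both arms: yes/no, severity, dates, and whether they led to dose reduction or stopping. Do so at the AE assessments already scheduled at V2, W10, W16, W26 and W52. V2 is needed to separate pre-existing constipation, headache or insomnia from new complaints; W52 because the flowchart marks both NB and an AE assessment there. State that this collection continues after week 12.
- Let the existing 12-week diary take these complaints too, so that W10 entries do not rest on recall alone.
- Name these data, with NB dose and reason for discontinuation, as the source for the tolerability endpoint.
- In 5.1.3.2, reconcile the week-12 bullet with the 24-hour paragraph, and say whether the bullet is the exception meant in 5.1.4.2. Which rule applies is for the sponsor to decide.

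The cost is one short checklist at five existing assessments, at most 310 in total. No visit and no Sponsor reporting of listed non-serious events is added, and the diary already exists.
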